5.2.3 Adverse Events of Special Interest

5.2.3.1 Neutropenia

Patients taking deferiprone were monitored for neutropenia, defined as a confirmed absolute neutrophil count (ANC) less than $1.5 \times 10^9/L$. Categories of neutropenia are as follows:

- Mild: A confirmed ANC $< 1.5 \times 10^9/L$ but $\geq 1.0 \times 10^9/L$
- Moderate: A confirmed ANC $< 1.0 \times 10^9/L$ but $\geq 0.5 \times 10^9/L$
- Severe: A confirmed ANC $< 0.5 \times 10^9/L$. Severe neutropenia is also referred to as agranulocytosis.

For a case of neutropenia to be confirmed, there must be 2 consecutive counts, a maximum of 3 days apart, that are both less than the specified value. If both counts are below $1.5 \times 10^9/L$ but are not in the same severity category, a third count was required to determine the severity.

5.2.3.2 Infections

If the patient developed fever or any type of infection during the study, deferiprone was to be interrupted immediately and neutrophil count should be obtained and monitored more frequently (every 2 days if $ANC < 1.5 \times 10^9/L$). Patients should be advised to report immediately to their physician any symptoms indicative of infection such as fever, sore throat, and flu-like symptoms. Patients has been provided with an emergency services card with contact information, and the patient/legal guardian will be advised to carry this card at all times. In presence of confirmed fever and/or infection, they would be required to have their neutrophil counts tested as soon as possible and no later than 24 hours after the symptoms of infection was detected. Therapy with deferiprone could be re-initiated once all symptoms had been resolved and it was deemed safe by the investigator.

5.2.4 Laboratory Measurements

The following laboratory tests had been performed:

- **Hematology** (for Group 1, monthly throughout the study; for Group 2, weekly for the first 6 months, biweekly for the next 6 months, and monthly thereafter): hemoglobin, total WBC count, ANC, and platelet count
- **Biochemistry** (semi-annually; Visits 1, 3, 5, 7, and 9): total protein, GGT, lactate dehydrogenase (LDH), sodium, potassium, chloride, fasting glucose, total and direct bilirubin (indirect bilirubin will be calculated by the sponsor), AST, ALT, albumin, blood urea nitrogen, calcium, creatinine, uric acid, alkaline phosphatase, and amylase
- **Serology** (Visits 1 and 9): Hepatitis B and C and HIV testing
- **Urinalysis** (annually; Visits 1, 5, and 9): pH, specific gravity, glucose, protein, ketones, blood, and (if indicated by the dipstick results), sediment microscopy. If there is blood in the urine or three or more “plus signs” for protein, samples must be sent for microscopy.
- **Pregnancy** (quarterly; Visits 1–9): serum pregnancy test

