Schedule of treatment and specimen collection:	All patients will be scheduled to take deferiprone daily, 3 times a day, for up to 2 years. Safety and efficacy assessments will be conducted at the following time points: • Hematology: • Group 1: Monthly up to Visit 9 (End of Study) or the Early

Schedule of treatment and specimen collection (cont'd):

Termination visit

- Group 2: Weekly up to Visit 3 (Week 26), then biweekly up to Visit 5 (Week 52), then monthly up to Visit 9 (End of Study) or the Early Termination visit
- Biochemistry: Visit 1 and semi-annually up to Visit 9 or the Early Termination visit
- Serology: Visits 1 and 9
- Serum ferritin: Visit 1 and quarterly up to Visit 9 or the Early Termination visit
- Liver MRI scan: annually, at Visits 1, 5, and 9 or Early Termination visit
- Cardiac MRI T2* scan: annually, at Visits 1, 5, and 9 or Early Termination visit

Statistical methods:

Safety Analysis

The incidences of AEs and SAEs reported from the start of deferiprone therapy for all patients will be tabulated. For patients continuing on deferiprone, this time period will be from the start of LA38-0411 to the completion of LA38-EXT; while for those switching to deferiprone, it will be from the start of LA38-EXT to the completion of LA38-EXT. AEs will be summarized by worst severity and by relationship to the study medication. Time to onset and duration of all SAEs, of AEs of special interest such as neutropenia, agranulocytosis, increased ALT, and arthralgia, and of additional AEs that will be determined at the end of LA38-0411, will be analyzed as follows: 1) the mean time to the first onset and the mean time to the last recurrence will be calculated, and 2) the mean duration for the first episode and the mean duration for any recurrent episodes, excluding the first episode, will be calculated for all SAEs and such AEs.

The percentage of discontinuations due to AEs will be calculated, and the AEs leading to discontinuation will be summarized in a frequency table.

Laboratory data (hematology and chemistry) will be summarized using descriptive statistics for continuous variables and frequency tables for discrete variables. The incidences of out-of-range data that are seen for two consecutive measures will be tabulated, and the changes from baseline to the end of study will be presented in shift tables.

Efficacy Analysis

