1.2 Rationale

ApoPharma Inc. is currently conducting a 12-month trial, study LA38-0411, to assess the safety and efficacy of deferiprone in patients with SCD or other anemias that necessitate regular blood transfusions (excluding thalassemia syndromes, MDS, myelofibrosis, Diamond Blackfan anemia, and primary bone marrow failure). In that study, a planned 300 participants will be randomized in a 2:1 ratio to receive either deferiprone or deferoxamine. Assessments include weekly, biweekly, or monthly monitoring of absolute neutrophil count (ANC); monthly assessments of adverse events, hematology, biochemistry, and vital signs; quarterly assessments of serum ferritin; and semi-annual serology, ECG, liver iron concentration (LIC) as measured by MRI, cardiac MRI T2*, and quality-of-life questionnaires.

Patients who complete study LA38-0411will be invited to enroll in the current study, LA38-EXT, in which all participants will receive deferiprone. Participants will thus receive deferiprone for a total of either 2 years or 3 years, depending on which treatment was assigned in the earlier study. The long-term data obtained will provide additional information on the safety and efficacy of deferiprone in patients with sickle cell disease or other anemias.

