3 STUDY DESIGN

3.1 Description of Study Design

LA38-EXT is a 2-year prospective, multi-center, single-arm, open-label extension of study LA38-0411. All patients who complete the earlier study will be offered the opportunity to continue in the extension study, with the final visit of LA38-0411 being Visit 1 of LA38-EXT. Patients who had been treated with deferiprone during LA38-0411 (Group 1) will continue to receive deferiprone for an additional 2 years, while those who had been treated with deferoxamine (Group 2) will be switched to deferiprone. Dosage will be 25–33 mg/kg three times a day (t.i.d.).

Patients will have blood counts monitored regularly (monthly throughout the study for patients in Group 1; weekly for the first 6 months, biweekly for the next 6 months, and monthly thereafter for patients in Group 2), and will visit the site quarterly for assessments of safety and efficacy for up to 2 years. The schedule of study procedures is shown in Table 5.1, and details are provided in Section 5.1.

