6.3.4 Analysis of Safety

The incidences of AEs and SAEs reported from the start of deferiprone therapy for all patients will be tabulated. For patients continuing on deferiprone, this time period will be from the start of LA38-0411 to the completion of LA38-EXT; for those switching to deferiprone, it will be from the start of LA38-EXT to the completion of LA38-EXT. AEs will be summarized by worst severity and by relationship to the study medication. Time to onset and duration of all SAEs, of AEs of special interest such as neutropenia, agranulocytosis, increased ALT, and arthralgia: 1) the mean time to the first onset and the mean time to the last recurrence will be calculated, and 2) the mean duration for the first episode and the mean duration for any recurrent episodes, excluding the first episode, will be calculated for all SAEs and AEs of special interest.

The percentage of discontinuations due to AEs will be calculated, and the AEs leading to discontinuation will be summarized in a frequency table.

Laboratory data (hematology and chemistry) will be summarized using descriptive statistics for continuous variables and frequency tables for discrete variables. The incidences of out-of-range data will be tabulated, and the changes from baseline to the end of study will be presented in shift tables.

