14.3 Safety Analyses

14.3.1 Adverse Events

Table 14.3.1.1 Overall summary of adverse events – Safety population

Table 14.3.1.2 Summary of adverse events – Safety population

Table 14.3.1.3 Summary of most common adverse events ($\geq 5\%$ in total) – Safety population

Table 14.3.1.4 Summary of adverse drug reactions – Safety population

Table 14.3.1.5 Summary of most common adverse drug reactions ($\geq 5\%$ in total) – Safety population

Table 14.3.1.6 Summary of serious adverse events – Safety population

Table 14.3.1.7 Summary of serious adverse drug reactions – Safety population

Table 14.3.1.8 Summary of adverse events by causality – Safety population

Table 14.3.1.9 Time to the first onset of SAEs – Safety population

Table 14.3.1.10 Time to the first onset of AEs of special interest such as neutropenia, agranulocytosis, increased ALT, arthralgia – Safety population

Table 14.3.1.11 Time to the last recurrence of SAEs – Safety population

Table 14.3.1.12 Time to the last recurrence of AEs of special interest such as neutropenia, agranulocytosis, increased ALT, arthralgia – Safety population

Table 14.3.1.13 Duration of the first onset of SAEs – Safety population

Table 14.3.1.14 Duration of the first onset of AEs of special interest such as neutropenia, agranulocytosis, increased ALT, arthralgia – Safety population

Table 14.3.1.15 Duration of the last recurrence of SAEs – Safety population

Table 14.3.1.16 Duration of the last recurrence of AEs of special interest such as neutropenia, agranulocytosis, increased ALT, arthralgia – Safety population

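### The planned between-group p-values for increased ALT are confounded by sampling schedule: monthly ALT in Group 1's first deferiprone year, only Weeks 26 and 52 in Group 2's

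*SAP*

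**What the plan says.** - **Parent study.** Protocol 1.2 describes LA38-0411 as having "monthly assessments of adverse events, hematology, biochemistry, and vital signs".
- **Extension.** The Protocol synopsis gives "Biochemistry: Visit 1 and semi-annually up to Visit 9 or the Early Termination visit". SAP 5.2.4 gives the same schedule, "semi-annually; Visits 1, 3, 5, 7, and 9", and lists ALT in the panel. By the visit table these are Weeks 0, 26, 52, 78 and 104. Patients "will visit the site quarterly for assessments of safety and efficacy for up to 2 years" (Protocol 3.1).
- **Counting window.** SAP 6.3.4 sets Group 1's window thus: "For patients continuing on deferiprone, this time period will be from the start of LA38-0411 to the completion of LA38-EXT". Group 2's window covers the extension alone. The windows are therefore about 3 and 2 years.
- **Analysis.** SAP 6.3.4 asks for time to onset and duration of "AEs of special interest such as neutropenia, agranulocytosis, increased ALT, and arthralgia". Table 14.3.1.10 is titled "Time to the first onset of AEs of special interest such as neutropenia, agranulocytosis, increased ALT, arthralgia"; Tables 14.3.1.12, 14.3.1.14 and 14.3.1.16 cover last recurrence and duration. The shells set DFP+DFP beside DFO+DFP, with Fisher's exact test for AE incidence (Tables 14.3.1.1 to 14.3.1.7) and a t-test for time to onset and duration.
- **Confirmation.** The biochemistry shells (Tables 14.3.6.2.1 and 14.3.6.2.2) have rows for Months 1 to 12, then 18, 24, 30 and 36, which matches monthly then semi-annual sampling.

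Neither document aligns the two schedules for the ALT analyses or names the difference as a limitation.

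**The concern.** Increased ALT is a laboratory finding. A rise without symptoms is found only if blood is drawn while it lasts, and it can be dated no earlier than that draw. In the first year on deferiprone, Group 1 had about twelve scheduled chances of detection and Group 2 had two, the first at Week 26. A short rise that is recorded in Group 1 can pass unseen in Group 2, and a lasting rise is dated later in Group 2.

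Increased ALT is a named event of special interest under the primary, safety objective. A small p-value could be read as a difference between continuing and switching patients when it reflects the sampling calendar. Any pooled ALT rate, such as the one behind the 5%-in-total cut-off of Tables 14.3.1.3 and 14.3.1.5, would also mix two levels of ascertainment.

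**Working it through.** The documents state no detection rate, alpha or power on this point, so there is no plan figure to reproduce.

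**Inputs**
- Group 1, deferiprone year 1: monthly ALT, interval 52/12 = 4.33 weeks (Protocol 1.2).
- Group 2, deferiprone year 1: ALT at Weeks 26 and 52, interval 26 weeks (SAP 5.2.4 and Table 1).
- Assumptions: duration d of the rise (range shown), onset spread evenly over the year, scheduled samples only, same true risk in both groups.

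**1. Detection in year 1.** Probability that a rise meets a scheduled test = min(1, d/interval).

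| Assumed duration | Group 1 | Group 2 |
|---|---|---|
| 2 weeks | 2/4.33 = 46% | 2/26 = 8% |
| 4 weeks | 4/4.33 = 92% | 4/26 = 15% |
| 8 weeks | 100% | 8/26 = 31% |
| 13 weeks | 100% | 13/26 = 50% |
| 26 weeks or longer | 100% | 100% |

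**2. Dating in year 1.** A persistent rise is first seen on average half an interval late: 4.33/2 = 2.2 weeks v 26/2 = 13.0 weeks. Mean recorded onset is the mean of the sampling times: 4.33 × 6.5 = 28.2 weeks v (26 + 52)/2 = 39.0 weeks, against a true mean of 26. The shift is 10.8 weeks with no true difference.

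**3. Effect on the p-values, year 1 only.** Further assumptions: 200 v 100 patients (the planned 300 split 2:1, a maximum because extension enrolment is not given), two-sided 0.05, true risk 7.6% (borrowed from the 54/712 adverse-reaction rate in Protocol 1.3).
- Observed incidence would be 7.0% v 1.2% (4-week rises), 7.6% v 2.3% (8-week) or 7.6% v 3.8% (13-week).
- By simulation, Fisher's test gives p < 0.05 in about 61%, 41% and 19% of trials with no true difference.
- For persistent rises, the t-test on time to onset gives p < 0.05 in about 35% of trials with 15 v 8 events and 63% with 30 v 15.

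**4. Direction over the full windows.** Group 1 is sampled monthly in year 1, then at Weeks 78, 104, 130 and 156 of deferiprone (mean 117). Group 2 is sampled at Weeks 26, 52, 78 and 104 (mean 65). With even onset, Group 2's mean recorded onset is 65 weeks at any of these durations. Group 1's is a weighted mean of 28.2 (year 1) and 117 (years 2 and 3), the weights being the detection shares:
- 4 weeks: (0.923 × 28.2 + 2 × 0.154 × 117)/(0.923 + 0.308) = 50 weeks
- 8 weeks: (28.2 + 2 × 0.308 × 117)/1.615 = 62 weeks
- 13 weeks: (28.2 + 2 × 0.5 × 117)/2 = 73 weeks
- 26 weeks or longer: (28.2 + 2 × 117)/3 = 87 weeks

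Group 1 therefore appears earlier than Group 2 for short rises and later for long ones. With front-loaded onset (exponential, mean 26 weeks, simulated), Group 1 is earlier throughout: about 21 to 30 weeks v 39.

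**5. After alignment.** If only Months 6 and 12 are read in both groups, detection probability and the mean delay (13.0 weeks) are equal by construction, and the schedule-driven difference in year 1 is zero.

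**The case against.** **A reader might extend the point to all adverse events, because review moved from monthly to quarterly.** The documents do not support that. Patients keep a daily diary that includes adverse events (Protocol 5.1, Visit 1), are told to report events (Protocol 7.2.1.2), and onset is the event's start date rather than the visit date (SAP 6.1.1). A symptomatic event need not be dated at the quarterly visit. Nor does the point reach neutropenia, since Group 2 has weekly and then biweekly counts in its first deferiprone year.

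**A reader might infer that Group 1 must look worse and earlier.** That is not established. Step 4 of the working shows that the order of onset depends on duration and onset pattern, neither of which is given. For incidence, Group 1's window is a year longer, while only completers of LA38-0411 enter, so Group 1 patients who left the parent study early are absent.

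**The detection figures are an upper-end contrast.** A raised value becomes an event only if the investigator judges it clinically significant (Protocol 7.2.1.1 and 7.2.2), follow-up may include extra tests (7.2.1.2), and the SAP lists local laboratory data (16.2.25). Unscheduled tests would narrow the gap; their frequency is not given. This stands as a limit on size.

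**Restricting all ALT reporting to common times would cost too much.** This also stands. For 4-week rises and a 2:1 split, pooled year-1 detection would fall from (2 × 92% + 15%)/3, about 67%, to 15%.

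**These are exploratory p-values in an open-label extension.** True, and it keeps the priority modest. But the shells print them, and nothing beside them warns of the difference in sampling.

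**Conclusion.** The concern holds for ALT as a laboratory-detected event. The planned between-group p-values for its incidence, time to onset and duration are confounded by sampling schedule even with no true difference. Incidence is distorted in year 1 only for rises shorter than the 26-week gap; for longer ones the distortion is in dating, by about 11 weeks on average, and hence in recorded duration too. The schedules are stated in the documents. Rise duration, onset pattern, enrolled numbers and the absence of unscheduled tests are assumptions. Schedule is not the only difference between the groups: exposure length and completer selection also differ, and the net direction over the full windows should not be asserted. The change is worth making before the tables are run.

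**What to change.** Change the SAP only; no visit or monitoring change is needed.

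1. Keep all reported ALT events in the descriptive tables, by group.
2. Drop the between-group p-values for increased ALT in the AE incidence tables and in Tables 14.3.1.10, 14.3.1.12, 14.3.1.14 and 14.3.1.16.
3. State beside any pooled ALT figure that ALT was sampled monthly in Group 1's first deferiprone year and semi-annually otherwise.
4. If the groups are to be compared, add a supplementary table of the proportion with ALT above the laboratory's upper normal limit (the abnormal range already used in the shift tables) at the scheduled times shared on the deferiprone clock: Months 6 and 12, then 18 and 24. Group 1's values come from LA38-0411 and then LA38-EXT Weeks 26 and 52; Group 2's from LA38-EXT Weeks 26, 52, 78 and 104.

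The cost is a few lines of SAP text and one optional table. The supplementary table does not use Group 1's other monthly values, but these stay in the main tables.

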5.2.5 Other Safety Measurements

5.2.5.1 Physical Examination

At Visits 1, 5, and 9, the investigator or a qualified delegate performed a physical examination of the following organs and systems: head, ears, eyes, nose, throat and neck, respiratory system, cardiovascular system, gastrointestinal system, musculoskeletal system, central and peripheral nervous system, skin, thyroid, and general constitution.

5.2.5.2 Vital Signs

Temperature, heart rate, respiration rate, and systolic and diastolic blood pressure were measured at each visit.

Weight was measured at each visit, and height was measured at Visits 1, 5, and 9.

5.2.5.3 Electrocardiogram

A standard 12-lead ECG was performed at Visits 1, 5, and 9. As a minimum, the following parameters had been assessed: HR, PR, QRS, QT, QTcF, QTcB. The results were interpreted by the investigator, and the overall interpretation had been documented.

5.2.5.4 Concomitant Medications

Information about prior and concomitant medications was collected at each visit. The following was to be recorded in the source documents and eCRFs:

- Any medications that the patient continues to take during the trial
- Any medications that the patient starts to take during the trial

6 STATISTICAL ANALYSIS

6.1 Endpoints

6.1.1 Primary Endpoints

- Adverse events (AEs): Frequency, severity, time to onset (the start date of AE minus the start date of exposure to treatment), duration (the stop date of AE minus the start date of AE), and relatedness to study product
- Serious adverse events (SAEs): Frequency and relatedness to study product
- Number of discontinuations due to AEs

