9.4.1.4 Analysis of Safety

The incidences of AEs and SAEs reported from the start of deferiprone therapy for all patients will be tabulated. For patients continuing on deferiprone, this time period will be from the start of LA38-0411 to the completion of LA38-EXT; for those switching to deferiprone, it will be from the start of LA38-EXT to the completion of LA38-EXT. AEs will be summarized by worst severity and by relationship to the study medication. Time to onset and duration of all SAEs, of AEs of special interest such as neutropenia, agranulocytosis, increased ALT, and arthralgia, and of additional AEs that will be determined at the end of LA38-0411, will be analyzed as follows: 1) the mean time to the first onset and the mean time to the last recurrence will be calculated, and 2) the mean duration for the first episode and the mean duration for any recurrent episodes, excluding the first episode, will be calculated for all SAEs and such AEs.

The percentage of discontinuations due to AEs will be calculated, and the AEs leading to discontinuation will be summarized in a frequency table.

Laboratory data (hematology and chemistry) will be summarized using descriptive statistics for continuous variables and frequency tables for discrete variables. The incidences of out-of-range data that are seen for two consecutive measures will be tabulated, and the changes from baseline to the end of study will be presented in shift tables.

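### The AE duration rule gives no value for an unresolved event and zero for a same-day event, and the recurrence tables do not report the mean that the text plans

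*SAP*

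**What the plan says.** Protocol 9.1.1 and SAP 6.1.1 both list AE duration within the primary endpoint. The SAP adds the formula: "duration (the stop date of AE minus the start date of AE". It does not say what to do when there is no stop date.

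SAP 6.3.4 plans two duration summaries for SAEs and AEs of special interest. One is "the mean duration for the first episode". The other is "the mean duration for any recurrent episodes, excluding the first episode, will be calculated for all SAEs and AEs of special interest". Protocol 9.4.1.4 plans the same second quantity: "the mean duration for any recurrent episodes, excluding the first episode, will be calculated for all SAEs and such AEs".

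The table list in SAP 14.3.1 contains "Table 14.3.1.13 Duration of the first onset of SAEs" and its counterpart for AEs of special interest (14.3.1.14). It then gives "Table 14.3.1.15 Duration of the last recurrence of SAEs" and the counterpart 14.3.1.16. In SAP section 17 these tables show N, mean, SD, minimum, maximum and a between-group t-test p-value.

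Under Protocol 7.2.1.2, follow-up of an AE may end at stabilisation, another explanation or loss to follow-up, as well as at resolution. Protocol 4.5 asks for an attempt at 30 days of outcome follow-up after withdrawal. Under SAP 6.3.4 the AE period starts with LA38-0411 for Group 1 and with LA38-EXT for Group 2. That is about three years and two years.

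**The concern.** There are three separate weaknesses.

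- **Unresolved events.** Because follow-up may end without resolution, some AEs will have no stop date. The subtraction then returns nothing, and a programmer working from the SAP alone would most naturally average the events that have a value. Long events are the ones most likely to be unresolved, so the mean is pulled down. The pull is stronger in the group with the shorter window, and the shells compare the two groups with a t-test.
- **Recurrences.** The text plans a mean over all episodes after the first. The tables pick one episode per patient, the last. An episode still open at the end of observation is usually the patient's last, so this choice also concentrates the first problem.
- **Same-day events.** Plain subtraction gives 0 days to an event that starts and stops on one date.

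At stake is the duration component of the primary safety description. Incidence, severity, relatedness and discontinuations are not affected.

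**Working it through.** The documents give no duration figure, so there is nothing to reproduce. The checks below use the documents' rules and, where stated, assumed inputs.

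**1. Day count.** An inclusive count is stop − start + 1, so the SAP formula is always 1 day lower. The relative shortfall is 1 divided by the inclusive mean: 50% at 2 days, 33% at 3, 20% at 5, 10% at 10 and 3.3% at 30.

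**2. Resolved events only.** From the documents: window T of 728 days (Group 2, 104 weeks) or 1092 days (Group 1, 156 weeks), and a follow-up tail F of 0 or 30 days. Assumed: onset uniform over T, exponential durations with mean m of 30, 90 or 180 days, and no early withdrawal. Let a = exp(−F/m) and b = exp(−(T+F)/m).

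- Proportion ongoing: p = (m/T)(a − b)
- Resolved-only mean: [m − mp − (m/T){(F+m)a − (T+F+m)b}] / (1 − p)

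Example with m = 180, T = 728, F = 0: a = 1 and b = exp(−4.044) = 0.0175.

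- p = 0.2473 × 0.9825 = 0.243
- Numerator = 180 − 43.7 − 0.2473 × (180 − 908 × 0.0175) = 95.7
- Mean = 95.7 / 0.757 = 126.4 days, which is 29.8% low

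| T (days) | F (days) | m = 30: mean (bias) | m = 90: mean (bias) | m = 180: mean (bias) |
|---|---|---|---|---|
| 728 | 0 | 28.7 (−4.3%) | 77.3 (−14.1%) | 126.4 (−29.8%) |
| 728 | 30 | 29.1 (−3.1%) | 78.4 (−12.9%) | 129.0 (−28.3%) |
| 1092 | 0 | 29.2 (−2.8%) | 81.9 (−9.0%) | 145.1 (−19.4%) |
| 1092 | 30 | 29.4 (−2.0%) | 82.5 (−8.4%) | 146.4 (−18.6%) |

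A simulation of 1,000,000 events per cell agrees within its error. With a 30-day tail, 1.5%, 8.9% and 20.6% of events are ongoing in the 728-day window. In the 1092-day window the figures are 1.0%, 5.9% and 13.9%. At an assumed mean of 7 days the bias is at most about 1%.

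**3. Between groups.** Give both groups the same true mean and a 30-day tail. At 180 days the resolved-only means differ by 146 − 129 = 17 days. At 90 days they differ by 82.5 − 78.4 = 4.1 days. The gap comes only from length of observation.

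**4. Does censoring remove it?** Total observed event time divided by the number of resolved events returned 30.0–30.1, 90.0–90.1 and 179.4–180.0 days in the simulation. Under the exponential assumption the bias disappears.

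**5. Text against tables.**

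| Planned in SAP 6.3.4 | Tables | Match |
|---|---|---|
| First episode | 14.3.1.13, 14.3.1.14 | Yes |
| All episodes after the first | 14.3.1.15, 14.3.1.16 (last recurrence) | No |

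An invented example has three patients with episode durations, in order, of 10/4/4/20, 5/6 and 8/30/10/2 days. The planned mean is (4+4+20+6+30+10+2)/7 = 76/7 = 10.9 days. The tabulated mean is (20+6+2)/3 = 28/3 = 9.3 days. The two can differ only if some patient has at least two recurrences.

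**The case against.** A reader might infer that the SAP excludes ongoing AEs, or that its rule always biases duration downward. The documents support neither: the SAP is silent, and imputing an end date is not ruled out. The silence still matters, because the choice changes the result. In the worked example, substituting the cut-off date gives 180 × 0.757 = 136 days, against 126 for resolved events only and a true mean of 180.

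A reader might also infer that the tables cover the last recurrence and nothing else. They do not: 14.3.1.13 and 14.3.1.14 report the first episode as planned. SAP sections 14 and 17 also allow tables to be added and shells to change. That makes correction easy, but no listed table yet carries the planned recurrence mean.

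The size is open to challenge. No document gives a duration distribution, and Protocol 7.2.1.2 and 7.2.1.7 can carry follow-up past 30 days, which would shrink the bias. Early withdrawal shortens observation and works the other way. The figures show the order of magnitude and do not predict the result.

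The day-count objection largely stands. Duration is tabulated only for SAEs and AEs of special interest, and neutropenia needs two counts to confirm. The offset is the same in both groups. A same-day SAE remains possible, because Protocol 7.2.1.5 counts a formal admission that need not be overnight.

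Finally, the protocol specifies a mean, so replacing it with a median would itself depart from the plan. That is right, and the median should be an addition.

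**Conclusion.** The point holds in limited form. For a primary endpoint component, the SAP leaves unresolved events without a value. If they are simply left out, mean duration is low by about 2–4%, 8–14% and 19–30% at true means of 30, 90 and 180 days. The ranges cover two- and three-year windows and tails of 0 and 30 days, and rest on assumed exponential durations, uniform onset and no withdrawal. For short events the effect is negligible. The unequal windows add an artificial group difference, about 17 days at a true mean of 180 days with a 30-day tail.

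The mismatch in Tables 14.3.1.15 and 14.3.1.16 needs no assumption: the planned recurrence mean is not among the listed outputs. The missing day is minor. The changes are worth making before the tables are programmed, but no formal decision in this single-arm extension rests on AE duration.

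**What to change.** 1. Retitle and reprogram Tables 14.3.1.15 and 14.3.1.16 as *Duration of recurrent episodes (excluding the first)*, to match SAP 6.3.4 and Protocol 9.4.1.4. State whether the mean is taken over episodes or patients, since one patient may contribute several correlated episodes.
2. In SAP 6.1.1, state that an AE without a stop date is censored at last contact. Show the number ongoing in each of Tables 14.3.1.13 to 14.3.1.16. Keep the planned mean, labelled as resting on resolved events, and add a Kaplan-Meier median where it can be estimated.
3. Define duration as stop minus start plus 1 day. Time to onset in the same sentence of SAP 6.1.1 is also a plain subtraction, so state the day convention for both.

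The cost is SAP wording and minor programming, with no new data collection. Stated durations become slightly longer, and medians may not be estimable for rare terms.
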